7.12 Clarification of “Other Action Taken”

The investigator will indicate the specific treatment provided as a result of the Adverse Event (this does not include diagnostic tests or referrals).

7.13 Clarification of Adverse Events Related to Study Procedures

Any untoward event that occurs from the beginning of the IUS insertion procedure until completion of insertion, or from the beginning of the removal procedure until the completion of removal, will be reported as an AE. Bleeding and cramping/pain occurring during IUS insertion or removal will be recorded on the IUS Insertion and Removal CRFs, as appropriate. Any other insertion or removal AEs should be recorded on the AE CRF with a causality assessment of “related to IUS procedure.” If any AE meets the definition of a Serious Adverse Event, even if it is recorded on the diary or Insertion or Removal CRF, it should also be reported on the AE and SAE CRFs and submitted to Sponsor.

7.14 Follow-up of Adverse Events and Serious Adverse Events

All AEs and SAEs must be followed through the Safety Follow-up, and any IUS or IUS procedure related AEs or SAEs followed until resolution, or until the condition stabilizes, or until all queries are resolved, or until the subject dies or is lost to follow-up (including withdrawal of consent). The Investigator is responsible to ensure that follow-up includes any supplemental investigations as may be indicated to elucidate as completely as practical the nature and/or causality of the AE/SAE. This may include additional laboratory tests or investigations, histopathologic examinations, or consultation with other health care professionals. Follow-up information should be submitted to the Sponsor in a timely manner as the information is obtained.

7.15 Clarification in Reporting of Deaths

All subject deaths (regardless of relationship to study drug) should be reported that occur from the signing informed consent through declaring the subject as a screen failure or Visit 8/Early Discontinuation and the post-Treatment Phase safety contact (if applicable). The information should be recorded on the Subject Death form and the SAE form.

Death is an outcome of an adverse event and not an adverse event itself. All reports of subject death should include an adverse event term (other than “death”) for the cause of the death. Since reporting of an SAE is required within 24 hours of discovery, death can be reported as an initial event term and updated to the final diagnosis in a follow-up report. If an adverse event term is not provided, the Investigator will be queried to obtain the cause of death. Only in the rare occurrence that no verbatim description of an adverse event can be obtained from the investigative site will “Death – Unknown Cause” be used as the event term.

7.16 Post-Study Treatment Reporting Requirements

For all enrolled subjects, all AEs and SAEs, regardless of cause or relationship that occur from IUS discontinuation through the Safety Follow-up require reporting to the Sponsor. In addition, if the Investigator learns of any SAE at any time after a subject has discontinued study drug, and such event seems reasonably related to study drug, the Investigator should promptly notify the Sponsor.

7.17 Subject Withdrawal

7.17.1 Criteria for Withdrawal of Subject from Treatment

The following criteria will be used to determine when a subject should be withdrawn from treatment (removal of study IUS):

- Subjects may choose to discontinue IUS use at any time during the study
- Subjects who become pregnant during study participation will have the IUS removed
 - Subjects who become pregnant during study treatment will continue to be followed until pregnancy completion or termination to determine health-related outcomes of the pregnancy
 - The Investigator will provide pregnancy outcome information as a follow up to the initial pregnancy reporting form
- When IUS perforation occurs during insertion or while on treatment, the IUS will be removed and the subject will be discontinued
- Subjects who experience an IUS expulsion (partial or complete) unless a second study IUS can be inserted within 2 weeks (one-time only) and reinsertion occurs at least 7 days prior to and not during either treatment Cycle 3 or Cycle 6
- The Investigator or Sponsor may discontinue a subject from treatment for other reasons. These may include, but are not limited to, the following:
 - Noncompliance with return visit schedule, diary completion, or use of an excluded therapy
 - A clinically significant IUS-related adverse event or the development of a new significant medical condition that compromises the subject's ability to participate in the study
 - Determination that it is not in the subject's best interest to continue treatment

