7.1.3.3 Effects on gestation and offspring

When pregnancy continues with the LNG20 IUS in place, the risks of long-term effects on the offspring are unknown. Based on data from copper IUDs, pregnancies that continue are at an increased risk of pre-term (<37 weeks) delivery as compared to women who conceive without an IUD in place (Ganer et al., 2009). The risk is highest if the IUD is not removed (18%) as compared to if the IUD is removed (14%); the risk in the general population is around 7%. Additionally, pregnancies that continue are also at a higher risk of being complicated by chorioamnionitis; 7% if the IUD remains, 4% if the IUD is removed, and slightly less than 1% in the general population (Ganer et al., 2009). It is unknown whether these risks are similar for women who conceive while using a LNG IUS.

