17. APPENDIX F: MANAGEMENT OF PREGNANCY

Among women who conceive with an IUS *in situ*, the spontaneous abortion rate is two-fold higher than that of the general obstetric population. A retained IUS also increases the risk of several late gestational adverse maternal and neonatal outcomes; this risk is reduced, but not eliminated, with early removal of the IUS.

For any subject who has a positive urine pregnancy test, the pregnancy should be confirmed by ultrasonography and serum hCG testing. The location of the pregnancy must be determined (intrauterine or extrauterine) using ultrasonography. Determine the location of the IUS using physical examination, ultrasonography and/or radiography as appropriate.

1. Management of intrauterine pregnancy with IUS in place

The following steps may be considered in the evaluation and management of intrauterine pregnancy in a subject with an IUS *in situ*:

- First trimester intrauterine pregnancy:
 - If the IUS strings are visible on speculum examination, remove the IUS to decrease the risk of subsequent miscarriage and infection. Antibiotics are unnecessary.
 - If the strings are not visible and the patient wishes to continue the pregnancy, remove the IUS under ultrasound guidance using an alligator forceps or an IUS hook. Removal can also be attempted by hysteroscopy. Data on hysteroscopic removal of IUS in early pregnancy are limited; therefore, it is not clear whether this technique poses greater or lesser risk of pregnancy loss than instrument removal under ultrasound guidance. Antibiotic prophylaxis is recommended when instrument removals are performed during pregnancy, including when IUS removal is to be followed by pregnancy termination (see below). The IUS may be left *in situ* if findings on ultrasound examination suggest removal will be difficult or disrupt the pregnancy (e.g., IUS embedded in the placenta or membranes).
 - If the woman desires pregnancy termination, IUS removal can be performed at the time of the termination. Manual or electric vacuum aspiration or an instrument such as an IUS hook, alligator forceps, ring forceps, or ovum forceps can be used to remove the IUS.

- In the setting of spontaneous abortion with IUS in place, it is recommended to remove the IUS and prescribe antibiotics (e.g., doxycycline 100 mg twice a day or ampicillin 500 mg four times a day for seven days).

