- Second trimester pregnancy —Counsel subject if the IUS remains *in situ*, that there is an increased risk of preterm labor and delivery (fourfold increase), second trimester fetal loss, and infection, but no proven increase in risk of birth defects. Removal of the IUS may cause rupture of membranes, bleeding, pregnancy loss, or fetal trauma; however, if the IUS is removed or expelled without complications, there is no increased risk of miscarriage.
 - Given this information, for pregnancies after 12 weeks, consider removing the IUS by pulling on the strings if the strings are visible and removal is unlikely to disrupt the placenta or membranes (based upon ultrasound localization of the IUS and placenta).
 - If the strings are not visible in the early second trimester, the IUS may be removed under ultrasound guidance if removal appears feasible, the IUS is not located behind the placenta, and it does not appear to be incorporated into the gestational sac. In particular, ultrasound guided removal is recommended in these cases if the IUS is in the lower uterine segment. If the IUS appears embedded in the placenta, located behind the placenta, or protrudes into the gestational sac, we suggest leaving the IUS *in situ*.
 - In the later second trimester, if the strings are not visible, the IUS should be left in place. The subject should be counseled that her risk of spontaneous abortion and premature delivery is increased relative to women whose IUSs may be easily removed.

2. Management of intrauterine pregnancy with extrauterine IUS

- If the IUS was expelled, the pregnancy should be managed as any other intrauterine pregnancy.
- If the IUS is extrauterine (perforation), the pregnancy should be managed without removal of the IUS until after the pregnancy is complete or, if applicable, at the time of cesarean delivery.

3. Management of extrauterine pregnancy

- Management should be performed within the local standard of care for the extrauterine pregnancy.
- If the IUS is intrauterine, the IUS should be removed and the subject discontinued from the study following appropriate safety follow-up.

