18. APPENDIX G: MANAGEMENT OF IUS ISSUES

1. Difficult Insertion

If insertion is difficult because the cervix cannot be properly visualized then the subject should have been excluded prior to randomization.

- If insertion is difficult because the uterus cannot be instrumented, the following measures are allowed:
 - Use of cervical anesthesia to make sounding and manipulation more tolerable
 - Use of rigid dilators to dilate the cervix if needed to allow passage of the sound.
If needed, a lacrimal duct probe or os finder may be used to start dilation.
 - Abdominal ultrasound guidance during dilation and/or insertion.

If the uterus still cannot be appropriately instrumented after the above measures are taken, or the uterus sounds to less than 5.5cm, then the subject should be considered an insertion failure and discontinued from the study. No further follow-up or visits are required.

2. Perforation

- Perforation may occur during insertion. The risk of perforation is increased in women with fixed retroverted uteri, during lactation, and postpartum. If during or after insertion there is clinical concern or exceptional pain or bleeding, appropriate and timely measures and assessments, such as ultrasound, should be performed to exclude perforation.
- Perforation or penetration of the uterine wall or cervix may occur during insertion although the perforation may not be detected until sometime later. The IUS must be located and removed; surgery may be required. Delayed detection of perforation may result in migration outside the uterine cavity, adhesions, peritonitis, intestinal perforations, intestinal obstruction, abscesses and erosion of adjacent viscera. Ensure a radiographic image of the entire abdomen is obtained to ensure the IUS hasn't migrated.
- If recognized and the IUS is intra-abdominal, a laparoscopy should be performed by a clinician experienced in such procedures to remove the IUS. Typically, minimal adhesions are present with intra-abdominal IUSs. If necessary, a laparotomy should be performed.

If the IUS is partially into or through the myometrium, it is reasonable to attempt removal with transcervical instrumentation. Initial attempts should be performed under ultrasound

guidance using an Alligator forceps (or similar instrument). If unsuccessful, attempts via hysteroscopy should be made before proceeding to laparoscopy.

3. Missing Strings

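### Protocol 7.17.1 and Appendix G.2 require IUS removal without exception, but Appendix F keeps the IUS in place or defers removal in some pregnancies, and nothing says which text governs

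*Protocol*

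**What the plan says.** Protocol 7.17.1, which lists the criteria for withdrawing a subject from treatment, has two unqualified rules. On pregnancy: "Subjects who become pregnant during study participation will have the IUS removed". On perforation: "When IUS perforation occurs during insertion or while on treatment, the IUS will be removed and the subject will be discontinued". Appendix G.2 agrees on perforation: "The IUS must be located and removed; surgery may be required". Neither place makes an exception for pregnancy or mentions Appendix F.

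Appendix F gives trimester-specific guidance:

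- First trimester, strings not seen, pregnancy continuing: removal under ultrasound guidance comes first, but "The IUS may be left *in situ* if findings on ultrasound examination suggest removal will be difficult or disrupt the pregnancy".
- Early second trimester, strings not seen, device in or behind the placenta or protruding into the sac: leaving the device is suggested.
- Later second trimester: "In the later second trimester, if the strings are not visible, the IUS should be left in place".
- Intrauterine pregnancy with a perforated device: "the pregnancy should be managed without removal of the IUS until after the pregnancy is complete", or until cesarean delivery where that applies.

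Section 7.1.3 speaks of removal more softly, tying it to usual medical practice, and points to Appendix F. Section 7.4 repeats the pointer.

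**The concern.** Two parts of one protocol give a site different answers for the same pregnant subject. The decision is whether, and when, to carry out an invasive procedure during a pregnancy, so it has to be made promptly and often by someone reading only one section. An investigator who opens 7.17.1 or G.2 finds a rule with no exceptions. One who opens Appendix F finds that the device stays for now in certain circumstances. Whichever text the site follows, a monitor reading the other could record a deviation. What is at stake is the consistency of a safety instruction, not the efficacy estimate.

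**Working it through.** No figure in the plan needs reproducing; the check is a comparison of texts, followed by a check that the situations can arise on study.

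**Comparison**

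| Situation | 7.17.1 (and G.2 for perforation) | Appendix F | Conflict |
|---|---|---|---|
| First trimester, strings visible | Remove | Remove | None |
| Termination, or spontaneous abortion with the device in place | Remove | Removal can be done at the termination; removal recommended after spontaneous abortion | None |
| Extrauterine pregnancy, device in the uterus | Remove | Remove | None |
| First trimester, strings not seen, removal difficult or disruptive | Remove | Leaving is permitted | Only if the site leaves it |
| Early second trimester, strings not seen, device in or behind placenta or in sac | Remove | Leaving is suggested | Only if the site leaves it |
| Later second trimester, strings not seen | Remove | Should be left | Direct |
| Perforation with intrauterine pregnancy | Remove and discontinue | Removal deferred | On timing |
| Perforation without pregnancy | Remove and discontinue | Not addressed | None |

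Only two of the eight rows give instructions that differ on their face. Two more differ if the site uses the latitude that Appendix F offers.

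**Can the second-trimester rows be reached?** Inputs are the Appendix B windows: Visit 6 from Day 28, Visit 7 on Days 85 to 105, Visit 8 on Days 169 to 189, with a pregnancy test at each. I assume conception just after a negative test and add 14 days for gestational dating.

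- All visits kept: 189 − 85 = 104 days; 104 + 14 = 118 days; 118 / 7 = 16.9 weeks at Visit 8.
- Visit 7 missed (Section 7.17.4.2 continues contact attempts to the next expected visit): 189 − 28 = 161 days; 161 + 14 = 175 days; 175 / 7 = 25.0 weeks at Visit 8.

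Both are past the 12 weeks at which Appendix F's second-trimester advice begins. Appendix F gives no cut-off for the later second trimester, so the documents do not settle whether 16.9 weeks falls there. These are extreme cases, not expected ones. Sections 7.4 and 7.17.1 also follow pregnancies to completion, so a subject whose device is left early stays within the conflict after Visit 8.

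**Is there a tie-breaker?** Sections 7.1.3 and 7.4 lead a reader to Appendix F, but neither says that it overrides 7.17.1 or G.2. I found no precedence statement for these texts.

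**The case against.** The strongest reply is that the working route already leads to Appendix F. The procedures for Visits 6, 7 and 8 send a positive test to 7.4, and 7.4 sends the site to Appendix F. Section 7.17.1 lists withdrawal criteria and is not the management section. Appendix F introduces its steps for a device in place as ones to consider, and where a perforated device coexists with pregnancy it postpones removal without waiving it, while 7.17.1 and G.2 set no deadline. All of this stands and lowers the practical risk. It does not remove the conflict: 7.17.1 and G.2 are written as absolute, and a reader has to infer the exception.

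The reply also disposes of four stronger readings that a reader might infer:

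- **That every perforation is in conflict.** It is not. Without pregnancy, 7.17.1 and G.2 agree and Appendix F is silent.
- **That a site breaches one text in any missing-strings pregnancy.** It does not. In the first trimester Appendix F starts with removal, and in the early second trimester it allows removal where that looks feasible. Removal in those situations satisfies both texts.
- **That a pregnant subject who keeps the device has no date for exposure or the continuation curve.** SAP 5.4 falls back on the Visit 8 date, the last known date of use or the last contact, and SAP 11.6 censors subjects without an event at last contact.
- **That the preterm-risk figures contradict each other.** Appendix F mentions a fourfold increase, and 7.1.3.3 gives 18% against about 7% (18 / 7 = 2.6). The latter are copper-device data on delivery before 37 weeks, which the protocol says may not carry over to a levonorgestrel device. Appendix F states neither source nor comparator. The two need not match, so no error is shown.

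**Conclusion.** The inconsistency holds in a narrow form. Sections 7.17.1 and G.2 are unconditional. Appendix F departs from 7.17.1 on whether to remove in the later second trimester with strings not seen. It departs from both on timing when a perforated device is found with an intrauterine pregnancy. In two earlier situations it allows a choice that 7.17.1 does not. No text settles the matter.

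The number of subjects affected should be very small. The 0 to 1 pregnancy is an assumption, and only some pregnancies would fall in the conflicting rows. The sample size and the primary analysis do not depend on it. The case for acting is that the instruction concerns a procedure in pregnancy and the remedy is cheap. I take no view on which clinical instruction is right.

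**What to change.** The sponsor should reconcile Protocol 7.17.1, 7.1.3, Appendix F and Appendix G.2 into one consistent instruction, covering pregnancy with the device in place and perforation found during pregnancy. It should state which text governs and have the other sections refer to it; at present 7.17.1 and G.2 carry no reference at all. The sponsor's medical lead should decide the clinical content. The cost is a wording amendment to the protocol, with IRB approval where required. It needs no new procedure, visit or data, and no change to the SAP.

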7.17.2 Withdrawal from the Study

The following criteria will be used to determine when a subject should be withdrawn from the study:

- A subject may withdraw consent for further participation in the study at any time without giving a reason

- A subject may choose to stop participation in the study for any reason. If the subject has not withdrawn consent and has an IUS in place they should be brought in for IUS removal and have appropriate safety follow-up procedures.
- A subject may also be discontinued from the study at the request of the Investigator or the Sponsor. If the subject has an IUS in place they should be brought in for removal and have appropriate safety follow-up procedures.
- Sponsor decision to terminate the study or discontinue the investigative site's participation

Reasons for subject withdrawal from the study should be documented in the subject's file and entered into the CRF.

Subjects that are designated as withdrawn from the study, lost to follow-up or who withdraw consent may not re-enter the study and no further data collection will occur.

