In the Treatment Phase subjects will continue to use only the study provided feminine hygiene products and record their bleeding on a daily diary. Feminine hygiene product collection will be limited to Cycle 3 and Cycle 6 during the Treatment Phase; no repeat collection is permitted. Study assessments will be performed at clinic visits at Treatment Phase Month 1 (Visit 6), and at the end of Cycle 3 (Visit 7) and Cycle 6 (Visit 8). Each visit will include a high sensitivity urine pregnancy test. Ferritin/hematology assessments and a subjective bleeding assessment using a VAS questionnaire will be performed at Visits 7 and 8. The IUS can be removed during the study when requested by the subject or when clinically indicated. At the end of 6 28-day cycles of use, unless medically contraindicated, study participants may opt to keep the IUS or otherwise it will be removed.

Participation will end at Visit 8 except for the following circumstances:

- The IUS was removed at Visit 8: these subjects will be contacted 7 to 10 days after the visit to assess bleeding and cramping after removal and any IUS-related or IUS procedure-related adverse events.
- Subjects with ongoing IUS-related adverse events after completion of the Treatment Phase that are not resolved or stabilized will have monthly contacts or visits, as appropriate, until the event is resolved or stabilized.

Routine safety monitoring (including clinically indicated physical exams, adverse event assessments, and vital signs) will be conducted for all subjects.

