6.10 Study Treatment Phase Completion/Early Discontinuation (Visit 8)

- Timing:
 - Completion of 6 cycles of LNG20 IUS use
 - Ideal: Day 169 to Day 174 (within 5 days of completing 6 cycles)
 - Allowable: up to Day 189 allowed (up to 21 days after completing 6 cycles)
 - Early discontinuation
- Procedures:
 - Review of adverse events or changes in medical history since the prior visit
 - Review of concomitant medications
 - Inquire about change in sexual partner
 - Collect and review daily diary for completeness

- Subject completion of Treatment VAS questionnaire
- High sensitivity urine pregnancy test (if positive, see Section 7.4)
- Weight, pulse and blood pressure
- Any clinically indicated physical examination
- Clinically verify presence of IUS by palpation or direct visualization of strings (for missing strings management see Section 6.13 and Appendix G)
- Chlamydia and gonorrhea testing for any subject following a change in sexual partner since the last study visit.
 - Women with positive tests should be contacted and receive treatment as soon as possible
- Breast and pelvic exam (if not performed within the last 3 months)
- IUS removal
 - If participant has contraindication to continuing IUS use or desires removal then perform IUS removal procedure
 - If no indication for removal, discuss option of continuing IUS or removal; remove IUS for all women that desire to discontinue IUS
- Retain all removed or expelled IUSs as described in the Study Reference Manual
- Collection of feminine hygiene products:
 - If completed full protocol: collect all products collected between Day 141 and Day 168
 - If early discontinuation coinciding with Visit 7 (Cycle 3): collect all products collected between Day 57 and Day 84
 - If early discontinuation not coinciding with a complete Visit 7 or Visit 8 collection window: no product collection
- If collected feminine hygiene products:
 - Interview subject for feminine hygiene collection compliance
 - Collect venous blood for:
 - hemoglobin/hematocrit and ferritin (if not obtained within the prior 6 weeks)
 - AH assay sample

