13. APPENDIX B: SCHEDULE OF EVENTS ENROLLMENT AND FOLLOW-UP

ASSESSMENTS	ENROLLMENT	TREATMENT					7-DAY FU CONTACT ⁶	ADDITIONAL FOLLOW-UP ⁷
	VISIT 5	VISIT 6	CONTACT	VISIT 7	CONTACT	VISIT 8 or ED		
	IUS INSERT	DAY 28-42	DAY 50-56	DAY 85-89 ²	DAY 133-140	DAY 169-174 ²	7-10 DAYS AFTER IUS REMOVAL	AS NEEDED
Blood Pressure/Pulse	X	X		X		X		
Weight	X	X		X		X		
Medical History	X							
Urine Pregnancy Test	X	X		X		X		
Breast Exam						X		
Pelvic Exam	X					X		
Gonorrhea/Chlamydia	X ¹	X ¹		X ¹		X ¹		
Hemoglobin/Hematocrit, Ferritin	X			X		X ³		
Venous blood for AH Analysis				X		X		
Confirm Eligibility	X							
Instruct/Dispense Diaries	X	X		X				
Instruct/Dispense Sanitary Products	X	X		X				
Instruct/Dispense Collection Kit		X		X				
Collect Sanitary Products/Collection Kit/Assess for Compliance				X		X		
Collect Diary/Assess for Compliance	X	X		X		X		
VAS Questionnaire	X			X		X		
Insertion of IUS	X							
Review of Adverse Events	X	X		X		X	X	X
Review Concomitant Meds	X	X		X		X	X	X
Verify IUS Presence		X		X		X		
Removal of IUS							X ⁴	
Schedule Next Visit/Contact	X	X		X		X ⁵		
Remind when to collect Products			X		X			
Confirm Next Visit			X		X			

¹ Test indicated only if change in sexual partner

² Visit to occur ideally within the 5 day window but may be up to 21 days (V7 window Days 85-105; V8 window Days 169-189)

³ If not collected within 6 weeks

⁴ As applicable; subject may keep IUS if not contraindicated

⁵ If has IUS removed

⁶ For subjects with IUS removed

⁷ For ongoing IUS or IUS removal-related AEs

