11.6 Continuation, Expulsion, and Removal Rates

Cumulative rates of IUS continuation, expulsion, and safety-related removal at 1 month (Visit 6), 3 months (Visit 7) and 6 months (Visit 8) will be summarized and analyzed using Kaplan-Meier methods. Time to event will be calculated as the date of continuation/expulsion/removal minus the date of IUS insertion plus one. Subjects without a continuation/expulsion/removal will be censored at the last contact date (as described in [Section 5.4](#)) and failure time will be calculated as the last contact date minus the date of IUS insertion plus one. Subjects who report an expulsion that is not confirmed by the study site will be censored. The safety-related removal rates may also be summarized by MedDRA preferred term in the same manner. Expulsion rates including analysis of complete and partial expulsions in the Safety Population will also be summarized.

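### Protocol 7.17.2 directs IUS removal for women who leave the study early, while Section 6.10 and Appendix B let them keep it, so the same exit may count as a removal or as a censored continuer

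*Protocol*

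**What the plan says.** Protocol 7.17.2 deals with leaving the study. For a woman who chooses to stop, whatever her reason, it says "If the subject has not withdrawn consent and has an IUS in place they should be brought in for IUS removal". For a woman discontinued at the request of the investigator or sponsor it says "If the subject has an IUS in place they should be brought in for removal and have appropriate safety follow-up procedures". Neither sentence offers her the choice of keeping the device.

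Protocol 6.10 describes Visit 8. Its title and its timing list cover both completion of six cycles and early discontinuation, and one set of procedures follows. The IUS is removed if there is a contraindication or she wants it out. Otherwise the instruction is "If no indication for removal, discuss option of continuing IUS or removal; remove IUS for all women that desire to discontinue IUS". The list treats completers and early leavers separately for collection of hygiene products, but not for IUS removal.

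Appendix B has a column shared by Visit 8 and early discontinuation. The footnote on IUS removal reads "As applicable; subject may keep IUS if not contraindicated" and is not restricted to completers.

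The synopsis and Section 3 place the explicit option to keep the IUS at the end of six 28-day cycles.

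SAP 11.6 estimates cumulative continuation by Kaplan-Meier at Visits 6, 7 and 8. Its censoring rule is "Subjects without a continuation/expulsion/removal will be censored at the last contact date".

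**The concern.** Take a woman who moves away in month four, has no medical reason for removal and would like to keep the IUS. A site that reads 7.17.2 brings her in to have it removed. A site that works from the visit procedures in 6.10, or from the schedule in Appendix B, offers her the choice and lets her leave with it.

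Continuation during the Treatment Phase is a stated secondary outcome. A removal done only because a woman left the study says little about tolerability or satisfaction with the device. If it counts as an event it lowers the continuation rate, and by an amount that depends on which section each site happened to follow. For the woman, the conflict decides whether she keeps a device she wanted to keep.

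**Working it through.** **Text comparison for an early leaver with the IUS in place, consent not withdrawn, no contraindication and no wish for removal**

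| Place | Instruction | Limited to completers? |
|---|---|---|
| Protocol 7.17.2 | Bring in for removal | No; it concerns women leaving the study |
| Protocol 6.10 | Discuss keeping or removing | No; covers early discontinuation too |
| Protocol Appendix B footnote | May keep | No |
| Synopsis and Section 3 | Option to keep | Yes; end of six cycles |

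The first row conflicts with the second and third. The fourth is compatible with the first, but its limit is missing from 6.10 and Appendix B.

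**Size of the effect on the continuation rate**

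The documents give no expected continuation rate to reproduce. The sizing inputs do reproduce: 85/(1 − 0.15) = 100 enrolled, and 0.80 − 1.96 × √(0.80 × 0.20/85) = 71.5%, as in Protocol 9.1.

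Inputs:
- 100 insertions (Protocol 9.1; SAP Section 4).
- 15 early exits (the Protocol 9.1 ceiling) or 20 (the upper SAP figure).
- Assumed: exits evenly spread over Days 1 to 168, and everyone else followed through six cycles.
- Assumed: k of the exits are women whose handling depends on the section followed. The documents give no value for k.

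Kaplan-Meier continuation is the product of (1 − 1/r) over events, where r is the number at risk just before each event. If all 15 exits are events, the product is 85/100 = 85.0%, with standard error √(0.85 × 0.15/100) = 3.6 points.

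Recoding one exit from event to censored drops its factor (r − 1)/r, so the estimate is multiplied by r/(r − 1). The gain from one exit is 0.85/(r − 1). That is 0.85/99 = 0.9 point for the first exit and 0.85/85 = 1.0 point for the fifteenth.

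With recoded exits spread across the sequence:
- k = 1 (r = 93): 0.85 × 93/92 = 85.9%
- k = 3 (r = 100, 93, 86): 0.85 × 100/99 × 93/92 × 86/85 = 87.8%
- k = 5 (r = 100, 96, 93, 90, 86): 0.85 × 100/99 × 96/95 × 93/92 × 90/89 × 86/85 = 89.7%

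| Early exits | All events | k = 1 | k = 3 | k = 5 |
|---|---|---|---|---|
| 15 | 85.0% | 85.9% | 87.8% | 89.7% |
| 20 | 80.0% | 80.9% | 82.7% | 84.6% |

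**The case against.** A consistent reading can be built. The synopsis says that when the IUS comes out before Cycle 6, the Visit 8 procedures are done at the removal visit. Protocol 5.5 equates IUS discontinuation with Visit 8/Early Discontinuation. On that reading an early-discontinuation visit is a removal visit, the keep option belongs to completers, and 7.17.2 governs early leavers. This is reasonable, but neither 6.10 nor Appendix B says it, and those are the procedures and schedule that a site works from. The unclear scope stands.

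A reader might infer that Section 3 also contradicts 7.17.2. It does not. "The IUS can be removed during the study when requested by the subject or when clinically indicated" permits removal on those grounds without excluding others, and the sentence after it ties the keep option to the end of six cycles.

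The affected group is narrow. She must stop early, keep her consent in force, attend a visit, and neither need nor want removal. Pandemic absences fit poorly: SAP 10.1 discusses such women as lost to follow-up or consent withdrawn, and under Protocol 7.17.4.2 a woman who does not report for Visit 8 is considered lost to follow-up. This stands, and is why the number is probably small.

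The calculation is also generous in two ways. It codes every exit as an event, although the 15% ceiling includes dropouts whom SAP 11.6 would censor. With five such women the starting value would be 89.7%, and the gain per recoded exit would stay near 1 point. It also moves all k women together; if half were handled each way, the shift would roughly halve.

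Finally, an all-reason continuation rate is a legitimate descriptive estimate, and censoring study-exit removals brings its own assumption that such exits are uninformative. This stands, so the review does not ask for censoring as the main rule.

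**Conclusion.** The conflict between 7.17.2 on one side and 6.10 with Appendix B on the other holds. Under the assumptions above, each affected woman moves six-month continuation by about 0.9 to 1.0 point at 15 exits. Three women would move it by 2.8 points (87.8 − 85.0) and five by 4.7 (89.7 − 85.0), against a standard error of 3.6. The counts are illustrative.

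That one path gives an event and the other a censored time is the natural reading of SAP 11.6, but it is an inference. The section speaks of a date of continuation as if continuing were itself an event, and never states what ends continuation.

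Three stronger conclusions go beyond the documents:
- A reader might infer that every early leaver loses her IUS under 7.17.2. The text says women should be brought in, which does not guarantee removal, and the sentence on voluntary stopping excludes those who withdraw consent.
- A reader might see a defect in consent withdrawal changing the outcome. Protocol 7.17.5 allows no further study activity after withdrawal, so no removal visit could be required.
- A reader might infer that the main efficacy or safety results are at risk. The primary MITT analysis depends on MBL. A removal done only because of study exit is neither an expulsion nor a safety-related removal. None of these results is directly affected.

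What remains is a modest point about one descriptive secondary outcome and about uniform handling of women at exit.

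**What to change.** In the protocol, reconcile 7.17.2 with 6.10 and the Appendix B footnote, and align the synopsis and Section 3, so that one instruction covers early leavers who have no indication for removal and do not request it. Which instruction that should be is a clinical decision for the sponsor, and this review takes no position on it.

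In SAP 11.6:
- Define the event for the continuation curve.
- State how a removal done only because of study exit is coded, and how an early exit with the IUS still in place is coded.
- Report the continuation rate under the alternative coding of study-exit removals as a sensitivity result.

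Protocol 7.17.2 already requires the reason for withdrawal in the CRF, so no new data item should be needed. Someone should check that the reason categories, which the documents do not show, can separate leaving the study from wanting to stop the IUS. The cost is one protocol clarification, a few words in the SAP and one extra descriptive line in the output.
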